#### 7.4 Diagnostics by [Ga]-NeoBOMB1 Compared with Conventional Imaging

The diagnostic performance of [Ga]-NeoBOMB1 to malignancies (lesions) known to overexpress GRPR will be paralleled with comparable standard imaging modalities such as, but not limited to, FDG-PET. Positive and negative lesions by the two imaging techniques will be cross-tabulated overall and also by localization area on a lesion level and a patient level, where positivity will be assessed visually. Cross-tabulations will also be repeated splitting by GRPR positive and negative patients and also by primary tumor type of patients.

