# 3.4 Study population / Selection of subjects

## 3.4.1 Inclusion criteria

- 1. Subjects must be at least 18 years of age
- 2. Subjects must have signed and dated an informed consent prior to any study-specific procedures.
- 3. Subjects with histologically-confirmed tumour, for whom a recent biopsy (not older than 6-month-old) has been performed.
- 4. Dosimetry group:
  - Luminal breast cancer
  - Adenocarcinoma of the prostate
- 5. Non-dosimetry group:
  - Luminal breast cancer
  - Adenocarcinoma of the prostate
  - Small cell lung cancer
  - Non-small cell lung cancer
  - Colorectal carcinoma
- 6. At least one malignant lesion detected *via* functional or morphological imaging (PET combined to appropriate tracer according to tumour type (PET combined to appropriate tracer according to tumour type, CT, MRI) within 3 months prior to [Ga]-NeoBOMB1 administration.
- 7. The Eastern Cooperative Oncology (ECOG) performance status 0-2.
- 8. Subjects must agree to use highly effective methods of contraception (female partners of male participants should use highly effective methods of contraception) during the trial.

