The additional files consist of the additional tests performed on the patients such as hemograms, semi-quantitative urine analyses and organ volume measurements. This information is to be also anonymized and renamed with the assigned internal Patient IDs. This information will be sent in digital form as well as printed documents (for verification and control). All the electronic information (DICOM files, MS Excel files and PDF files) will be stored on DVDs (original and backup copy in case of having any trouble with the original one).

All other relevant info relative to patients must be sent to the central reading center, including the standard morphologic imaging study that has detected the malignancy or its recurrence, likely to be CT, MRI or PET, in DICOM format, with the same anonymization method used for the internal Patient IDs. An excel file will include specific info about such study, the date of acquisition, the protocol used, the injected tracer if pertinent, the scan duration, the reconstruction algorithm as well as the medical interpretation from the radiologist/nuclear medicine physician.

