### 5.4 Concomitant medication

Patients can be under active systemic treatment such as anti-cancer therapy or hormonal therapy. However, the IP administration should be done at least 72 hours after administration of chemotherapy, to allow for the resolution of any acute side effects. Chemotherapy administration or the start of a new anti-cancer therapy should also be held until 48hrs after IP administration.

Regional/local radiation should be completed at least 2 weeks before administration of IP. Focal radiation therapy is allowed after discussion with the study medical monitor.

The participation of patients on treatment with check-point inhibitors should be discussed with the study medical monitor, to assess concurrent adverse events and side effects prior to administration.

[figure not shown]
Any other allowed concomitant prescribed medications should be discontinued 2h before and until 4h after administration of [Ga]-NeoBOMB1.

[figure not shown]

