#### 7.4.2 Patient-Level Analyses of Diagnostics by [Ga]-NeoBOMB1 Compared with Conventional Imaging

At patient level, positive agreement of [Ga]-NeoBOMB1 will be defined as the proportion of patients with at least one positive lesion detected by conventional imaging (i.e. all patients included in the trial) who also have at least one positive lesion detected by [Ga]-NeoBOMB1 PET imaging

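### The conventional comparator scan may be up to 3 months old with treatment in between, and the agreement analyses have no check that separates disease change from tracer disagreement

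*SAP*

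**What the plan says.** **Age of the comparator.** Protocol 3.4.1, criterion 6, requires a malignant lesion on imaging, with the window given as "tumour type, CT, MRI) within 3 months prior to" injection. Protocol 4.1.6 sends to the central reading centre all relevant patient information, "including the standard morphologic imaging study that has detected the malignancy or its recurrence, likely to be CT, MRI or PET". SAP 7.4.2 takes as its denominator patients with "at least one positive lesion detected by conventional imaging (i.e. all patients included in the trial"), which ties the comparator to the inclusion imaging. Both schedules in Protocol 4.5 mention conventional imaging only as a footnote to the eligibility row. No section asks for a repeat comparator scan near the PET.

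**Treatment in the interval.** Protocol 5.4 states: "Patients can be under active systemic treatment such as anti-cancer therapy or hormonal therapy". On chemotherapy, it says that "the IP administration should be done at least 72 hours after administration of chemotherapy, to allow for the resolution of any acute side effects". On radiation: "Regional/local radiation should be completed at least 2 weeks before administration of IP". Focal radiation is possible after discussion with the medical monitor, with no interval given. The same section also asks that chemotherapy or a newly started anticancer therapy be held until 48 hours after injection.

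**Analysis.** SAP 7.4 states: "Positive and negative lesions by the two imaging techniques will be cross-tabulated overall and also by localization area on a lesion level". It continues with a patient-level table and splits by GRPR status and tumour type, with positivity judged visually. SAP 7.4.1 gives formulas for overall, positive and negative agreement, and SAP 7.4.2 defines patient-level positive agreement. None of them refers to the interval between scans or to treatment given within it.

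**The concern.** An agreement table between two imaging methods is informative about the tracer when both methods look at the same disease. Here the two looks can be 3 months apart, and the patient may have been treated between them. A lesion that has gone by the time of the PET, and a lesion that has appeared by then, each enter the table as a discordance.

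Estimating performance relative to standard imaging is a secondary objective, and the SAP reports it overall and by tumour type. The same comparison feeds the lesion counts in SAP 7.1. It also feeds SAP 7.5.3, where the proportion of conventional lesions also seen on NeoBOMB1 PET is plotted against GRPR expression. As the SAP stands, a reader of the report could not tell how much of any disagreement is the tracer and how much is change in the disease.

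**Working it through.** **The plan's own precision figure.** SAP 10 gives 66.4% to 92.7% for 25 of 30. It concerns sensitivity against histopathology, not this comparison, but it is the only precision figure available. The Wilson interval with p = 0.8333, n = 30 and z = 1.96 reproduces it:
- Centre: (0.8333 + 3.8415/60) / (1 + 3.8415/30) = 0.8974/1.1280 = 0.7955.
- Half-width: 1.96 × √(0.8333×0.1667/30 + 3.8415/3600) / 1.1280 = 0.1311.
- Limits: 66.4% and 92.7%.

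**How change in the disease enters the SAP 7.4.1 formulas.**
- Positive agreement = double positive / (double positive + comparator single positive). A lesion on the earlier scan that is tracer-negative at PET because of treatment moves from the first count to the second. A partly responding lesion that still takes up tracer does not move.
- Negative agreement = double negative / (double negative + comparator single negative). A site negative on the earlier scan and tracer-positive at PET because of progression moves from the first count to the second. It also leaves the numerator of overall agreement.

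**How it enters SAP 7.4.2.** Every patient is comparator-positive, and one tracer-positive lesion is enough to agree. Progression therefore cannot lower this measure. Response lowers it only if no tracer-positive lesion is left. One such patient is 1/50 = 2 percentage points overall, or 1/10 = 10 points within a tumour type.

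**Illustration of size. All inputs are assumed.** Let p be same-day positive agreement and f the share of comparator lesions that are tracer-negative at PET because of response, taken as independent of whether the tracer would have seen them on the scan day. Reported positive agreement is then p × (1 − f).

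| f | p = 85% | p = 100% |
|---|---|---|
| 5% | 80.8% | 95% |
| 10% | 76.5% | 90% |
| 20% | 68.0% | 80% |
| 30% | 59.5% | 70% |

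Let q be same-time negative agreement and g the share of double-negative sites that become tracer-positive. Then q × (1 − g) with q = 90% gives 85.5%, 81.0% and 72.0% for g = 5%, 10% and 20%.

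**Discordance test, also on assumed counts.** Start from 83 double-positive lesions and 17 discordant each way, an odds ratio of 1.0. If 10% of the 83 resolve, the split is 25 to 17 (17 + 8.3, rounded), odds ratio 17/25 = 0.68, exact p = 0.28. If 20% resolve, it is 34 to 17 (17 + 16.6, rounded), odds ratio 17/34 = 0.50, exact p = 0.024. The interval alone would create that apparent deficit. The p-values ignore clustering of lesions within patients, which the SAP acknowledges.

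**The case against.** Several points on the other side are fair.

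- **The comparator's identity is inferred.** No sentence says outright that the eligibility scan is the comparator. SAP 7.4 speaks of comparable standard modalities with FDG-PET as an example, and the reading-centre manual is a separate document. The inference from Protocol 3.4.1, 4.1.6 and 4.5 and SAP 7.4.2 is nevertheless strong, and nothing in the documents sets a shorter window.
- **Protocol 5.4 limits new therapy.** The hold on starting an anticancer therapy until after injection narrows what can happen in the interval. How far back it reaches is unclear. Ongoing systemic therapy and completed local radiation are plainly allowed, and that is enough for the point.
- **There are partial mitigations.** A low-dose CT accompanies each PET, but for attenuation correction and anatomical orientation; it is not named as the comparator. Routine follow-up data within 3 months (Protocol 4.4) are optional and address tracer foci with no morphological match, not lesions that have responded.
- **The objective is secondary and descriptive.** SAP 5 treats all tests as exploratory, and SAP 10 disclaims strong conclusions within tumour types. This limits the consequence. It does not make the estimate measure what it is named for.

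A reader might also infer that the tumour-type figures are invalid because treatment intensity differs between types. The SAP plans no comparison of agreement between tumour types, and the documents give no treatment rates by type, so that reading is not supported.

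**Conclusion.** The point holds as a gap in the agreement analyses. The comparator may be up to 3 months old, treatment in the interval is permitted, and SAP 7.4.1 and 7.4.2 score the resulting changes as disagreement. Lesion-level measures are exposed in both directions. Patient-level positive agreement is exposed only to response that leaves no tracer-positive lesion.

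The size is unknown. The fall from 85% to about 77% or 68% rests on assumed resolution of 10% or 20% of comparator lesions; the documents give neither the 85% nor any rate of change.

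Two stronger readings go too far. One is that every responding or new lesion counts against the tracer at every level; the formulas do not work that way. The other is that conclusions should rest only on untreated patients. If stable hormonal therapy counted as treatment, that subset could be very small among the 10 prostate and 10 luminal breast patients, and restricting to it would not deal with progression. A sensitivity analysis beside the full tables is the proportionate response.

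**What to change.** Amend the SAP before database lock, which SAP 1 allows. Keep the all-lesion and all-patient tables. Add to 7.4.1 and 7.4.2 a pre-specified sensitivity analysis of agreement that:

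1. excludes lesions irradiated or resected between the comparator scan and injection, and lists them; if the treated site is not recorded per lesion, flag the patient instead;
2. reports agreement separately for patients with and without systemic anticancer therapy newly started or changed, or chemotherapy given, in the interval, so that unchanged hormonal therapy alone does not count;
3. reports the comparator-to-PET interval in days by tumour type, and shows agreement for shorter versus longer intervals at a cut-point fixed in the SAP. This is the part that addresses progression.

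State that if these results differ materially from the all-patient table, the report will not attribute the disagreement to the tracer.

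The comparator acquisition date already goes to the reading centre (Protocol 4.1.6), and SAP 6.4 already covers cancer drugs, radiotherapy and surgery. The documents do not confirm that radiotherapy is recorded by site, hence the patient-level fallback in item 1. The cost is a few added tables with small numbers. No eligibility or treatment rule changes.

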## 7.4.1 Lesion-Level Analyses of Diagnostics by [Ga]-NeoBOMB1 Compared with Conventional Imaging

At lesion level, overall, positive, and negative agreement of [Ga]-NeoBOMB1 will be calculated based on the aforementioned tabulations as follows:

- Overall agreement = 100% x (Double positive + Double negative) / total number of patients who underwent both imaging procedures
- Positive agreement = 100% x Double positive / (Double positive + Comparator single positive)
- Negative agreement = 100% x Double negative / (Double negative + Comparator single negative)

The McNemars test may also be performed to assess the level of discordance between the two imaging techniques where appropriate, acknowledging issues with lack of independence of observations on a lesion level. The odds ratio and its confidence intervals (80% and 95%) will be computed for overall result and for each tumor type. The same calculation will be computed for GRPR positive and negative, if feasible.

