### Secondary endpoints:

- The [68Ga]-NeoBOMB1 bio-distribution, pharmacokinetics, dosimetry and absorbed • dose in critical organs will be determined by calculation of TACs measured by a Nal gammacounter from blood and urine and stability will be analysed using HPLC measurements. Regions of interest (ROI) for critical organs and tumour lesions will be drawn using the acquired images resulting in time-activity curves with quantitative fractions of administered activity. Dosimetry calculations will be issued from the analyses of organs receiving the highest dose, identified visually. ROI will be placed over these organs to determine relative radiotracer uptake calculated as a percentage of the injected dose per gram of tissue (%ID/g). Tissue activity curves will be generated from the amount of radioactivity in one given tissue at a given moment considering renal excretion activity. Tissue ACs will be fitted to mono- and bi-exponential curves to yield cumulative activities. Urine samples 0-2h and 4h post-injection will be collected to complete dosimetry and biodistribution assessments. The absorbed dose (µGy/MBq) will be transformed into formal biological equivalent dose for radiation exposure (µSv/MBq) to finally yield an effective radiation dose, a factor between others that could help providing an estimation of total danger to the whole organism. Effective radiation dose will be summarized descriptively.
- Tumour uptake will be evaluated by Standard Uptake Value. SUVmean and SUVmax will be determined and summarized descriptively.
- Number of observed tumour lesions and localization in PET/CT will be summarized descriptively overall and split by GRPR positive and negative patients, as well as by tumour type, and will be compared to the number of observed lesions and localization in a comparable conventional imaging.
- Positive and negative lesions by the two imaging techniques will be cross tabulated overall and also by localization area on a lesion level and a patient level. This will also be repeated splitting by GRPR positive and negative patients and also by primary tumour type of patients in the trial.
  - On a lesion level overall, positive and negative agreement of [Ga]-NeoBOMB1 will be calculated as follows:
    - Overall agreement = 100% x (Double positive + Double negative) / total number of patients who underwent both imaging procedures

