    - Positive agreement = 100% x Double positive / (Double positive + Comparator single positive)

 Negative agreement = 100% x Double negative / (Double negative + Comparator single negative)

The McNemars test may also be performed to assess level of discordance between the two imaging techniques where appropriate, acknowledging issues with lack of independence of observations on a lesion level.

- On a patient level positive agreement of [Ga]-NeoBOMB1 will be defined as the proportion of patients with at least one lesion detected by conventional imaging (i.e. all patients included in the trial) that also have at least one lesion detected by [Ga]-NeoBOMB1.
- [Ga]-NeoBOMB1 PET preliminary diagnostic performance relative to cytology and/or histopathology findings from archival and/or recent biopsy specimens will be assessed primarily on a patient level, but also on a lesion level for lesions with associated biopsy data available.
  - On a patient level, patients with at least one positive PET imaging lesion identified versus those without any PET imaging lesions identified will be crosstabulated with whether or not they have at least one biopsy with GRPR expression identified. Sensitivity and specificity values will be calculated as appropriate.
  - On a lesion level, positive and negative PET imaging lesions will be crosstabulated with their GRPR positive or negative status according to biopsy data and sensitivity and specificity values will be calculated as appropriate. Appropriate tests of association may also be performed if relevant.

Potential relationships between [Ga]-NeoBOMB1 PET targeting properties and cytology and/or histopathology findings may also be explored using alternative endpoints where appropriate. For example, continuous measures of GRPR expression may be correlated against each patient proportion of conventional imaging lesions also detected by [Ga]-NeoBOMB1 PET imaging using scatterplots and simple linear regression models.

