#### 7.5 Diagnostics by [Ga]-NeoBOMB1 Compared to Histological Evidence

The diagnostic performance of [Ga]-NeoBOMB1 to malignancies (lesions) known to overexpress GRPR will be compared with cytology and/or histopathology findings from archival and/or recent biopsy specimens.

Since the biopsy is only performed on one lesion, a direct link may not be possible if there are multiple lesions per organ identified on [Ga]-NeoBOMB1-PET. In this event, the determination of positive versus negative lesions on [Ga]-NeoBOMB1-PET will be done at organ level, i.e., if any lesion is positive in that organ, then the organ will be considered positive.

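### Lesion-level overall agreement divides concordant lesions by the number of patients, so it is not a proportion and scales with lesions per patient

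*SAP*

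**What the plan says.** SAP 7.4 plans to cross-tabulate lesions read as positive or negative by each technique, overall and "also by localization area on a lesion level and a patient level, where positivity will be assessed visually". Protocol 7.3 plans the same, "also by localization area on a lesion level and a patient level".

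SAP 7.4.1 then introduces three measures at lesion level, which "will be calculated based on the aforementioned tabulations as follows":

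- Overall: "Overall agreement = 100% x (Double positive + Double negative) / total number of patients who underwent both imaging procedures".
- Positive: double positives over double positives plus comparator-only positives.
- Negative: double negatives over double negatives plus lesions negative on the comparator alone.

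Protocol 7.3 gives the same three formulas, also at lesion level. SAP section 11, which lists departures from the protocol analyses, does not touch them.

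Protocol 3.3.2 and SAP 3.2 list overall, positive and negative agreement as secondary endpoints, by lesion and by patient. At patient level, however, Protocol 7.3 and SAP 7.4.2 define only positive agreement. Its base is patients with at least one lesion on conventional imaging, glossed in the SAP as "i.e. all patients included in the trial".

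**The concern.** The positive and negative formulas take numerator and denominator from the same lesion table. The overall formula alone puts lesions over patients. SAP 7.5 expects that some patients will have several lesions in one organ, so the two counts will generally differ. A programmer who follows the text would report a figure that mixes agreement with disease burden.

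A second gap sits beside it. Negative and overall agreement both use the double-negative count, and neither document says how a site negative on both techniques gets into the table. The organ rule in SAP 7.5 ("if any lesion is positive in that organ, then the organ will be considered positive") is written for the histology comparison only.

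At stake are listed secondary endpoints, reported overall and by tumour type.

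**Working it through.** **Inputs.** For one lesion table let a = double positive, b = NeoBOMB1-only, c = comparator-only, d = double negative, L = a+b+c+d, and N = patients with both procedures. The plan is 50 patients, 10 per tumour type (Protocol 7.1, SAP 10). Neither document gives lesion counts or an expected lesion-level agreement, so the values below are assumptions. There is no stated agreement figure to reproduce.

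**Step 1: the identity.** As written: 100 × (a+d)/N = 100 × [(a+d)/L] × (L/N). That is true agreement times lesions per patient, exactly. The two coincide only when L = N (or when nothing is concordant).

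**Step 2: size.** At 60% true agreement the formula gives 60 × L/N:

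| Lesions per patient | As written | Lesion denominator |
|---|---|---|
| 1 | 60% | 60% |
| 1.5 | 90% | 60% |
| 2 | 120% | 60% |
| 4 | 240% | 60% |

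It passes 100% once L/N exceeds 1/agreement: 2.5, 1.67 or 1.25 lesions per patient at 40%, 60% or 80%.

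**Step 3: ordering of tumour types.** Types A and B, with true agreements pA > pB, swap order when B's lesions per patient divided by A's exceeds pA/pB: 0.8/0.7 = 1.14, 0.8/0.6 = 1.33, 0.8/0.5 = 1.6. Example with 10 patients each: 9 concordant of 18 lesions shows 9/10 = 90% (true 9/18 = 50%), above 8 concordant of 10 lesions at 8/10 = 80% (true 80%).

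**Step 4: direction.** If every patient contributes at least one comparator lesion to the pooled table, L ≥ N and the figure equals or overstates agreement. If the formula were also applied to one localization area, L could be below N: 18 concordant of 20 lesions among 50 patients would show 18/50 = 36% against 18/20 = 90%.

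**Step 5: double negatives, denominator already corrected.** Take a = 60, b = 15, c = 25:

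| d listed | Overall | Negative | Positive |
|---|---|---|---|
| 0 | 60/100 = 60.0% | 0/15 = 0% | 60/85 = 70.6% |
| 50 | 110/150 = 73.3% | 50/65 = 76.9% | 70.6% |
| 200 | 260/300 = 86.7% | 200/215 = 93.0% | 70.6% |

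If only lesions seen by at least one technique are listed, d = 0. Negative agreement is then 0/b, which is 0%, or 0/0 when b = 0, whatever the tracer does. Overall agreement becomes a/(a+b+c), the share of detected lesions seen by both.

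**Step 6: patient level, all areas pooled.** Inclusion criterion 6 requires at least one lesion on prior imaging, so an eligible patient is comparator-positive. With 42 of 50 patients NeoBOMB1-positive, overall = (42+0)/50 = 84%, positive = 42/(42+8) = 84%, and negative = 0/0.

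**The case against.** **It is a slip that any analyst would correct and any reader would see.** In part this stands. The cross-tabulation is reported too, so the percentage can be recomputed. A correct overall agreement is also a weighted average of positive and negative agreement and must lie between them. With d = 0 and at least one comparator lesion per patient (a+c ≥ N), the written figure a/N is at or above positive agreement a/(a+c), whereas the correct a/(a+b+c) cannot exceed it. A reader might infer from Step 3 that wrong values below 100% would go unnoticed; where no double negatives are listed, that goes too far. With double negatives listed, it can happen. For N = 10, a = 4, b = 1, c = 6, d = 3, positive agreement is 4/10 = 40%, negative 3/4 = 75%, written overall 7/10 = 70% and true overall 7/14 = 50%. A silent correction would also leave the analysis at odds with the SAP.

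**Understatement by area is not an established defect.** A reader might infer it because SAP 7.4.1 points back to tables that include localization areas. But the Protocol synopsis names overall, GRPR status and tumour type as the splits for agreement, and Protocol 3.3.2 and SAP 3.2 name overall and tumour type. Agreement by area is not a listed endpoint, so the 36% example is conditional.

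**A listing rule may exist elsewhere.** Protocol 4.1.6 cites a separate central reading manual, which was not available. It is described there for data transfer, but it could hold such a rule. The gap is therefore claimed only for the protocol and SAP. The manual would not repair the denominator.

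**At patient level no wrong number arises.** This stands. Only positive agreement is defined there, so what remains is the wording of the endpoint list.

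**Conclusion.** The denominator is wrong as written in both documents. The error factor is exactly the number of lesions per patient; its actual size is unknown until lesion counts exist. At 60% agreement it turns 60% into 90% at 1.5 lesions per patient and 120% at 2. Tumour types can be misordered if their lesion burdens differ enough.

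A reader might infer that the figure can never fall below the true one. That holds only for the pooled table and only if every patient's comparator lesion enters it. Someone dosed despite an eligibility deviation, or a known lesion not assessable by both techniques, would break the condition.

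The missing rule for double negatives is a real but secondary gap: negative agreement has no fixed meaning until the listing is stated. The patient-level point is one of consistency only.

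This should be fixed, but its reach is limited. The measures are secondary, the analysis is descriptive and any testing is exploratory. Lesion-level positive agreement does not use N, b or d, and the McNemar odds ratio uses only b and c. The primary endpoint and sample size do not depend on any of this.

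**What to change.** 1. In SAP 7.4.1, make the denominator of overall agreement the total number of lesions assessed by both techniques, that is, the sum of the four cells of the same table. Record the change in SAP section 11 before database lock.
2. In the same edit, report lesion-level negative agreement only if a pre-specified listing of assessable sites exists, and cite it. If only lesions detected by at least one technique are listed, omit negative agreement and give positive agreement with the counts of comparator-only and NeoBOMB1-only lesions. State the listing next to overall agreement too, since it also depends on d.
3. In SAP 3.2, say that with all areas pooled only positive agreement is informative at patient level.
4. Align Protocol 7.3 and 3.3.2 at the next amendment.

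Replacing the lesion-by-lesion endpoint with a region-level one, or adding patient-level tables by area, is not needed to cure this defect.

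The cost is a few lines of SAP text. SAP section 1 allows revisions before lock, with reasons given in the SAP amendment and the study report, and section 11 already drops one listed comparison. The protocol wording can wait, because Protocol 12 requires approval before a substantial amendment is implemented. No new patients or scans are needed. The one possible loss is negative agreement at lesion level, if no site listing exists.
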